2.1.2 Introduction to Investigational Treatment

GEN1029 is an equimolar mixture of two non-competing DR5-specific humanized IgG1 κ antibodies, with an E430G HexaBody[®] mutation in their Fc domains. This is the first time that an antibody product exploiting Genmab's HexaBody technology will be tested in humans. HexaBody molecules are monomeric IgG1 antibodies that have an engineered Fc-region harboring a single mutation, such as E430G, that significantly enhances the natural process of forming ordered hexameric antibody structures through intermolecular Fc-Fc interactions upon cell surface antigen binding (de Jong et al., 2016; Diebolder et al., 2014). In the case of GEN1029, this results in DR5 hyperclustering and activation of the cell death inducing signaling pathway, leading to programmed cell death of the target cells.

The mechanism of GEN1029-mediated DR5 clustering through antibody hexamerization is different from conventional, bivalent DR5-specific IgG1 antibodies, such as conatumumab, tigatuzumab, drozitumab, lexatumumab, and LBY-135 that depend on additional Fc γ R-mediated crosslinking in order to induce DR5 hyperclustering and apoptosis. Despite promising preclinical activity and a generally good safety profile (for the majority of the compounds, the MTD was not reached – please also refer to the benefit-risk assessment in Section 2.3), these conventional IgG1 antibodies against DR5 failed to show convincing anti-tumor efficacy in clinical trials (Amarante-Mendes et al., 2015; Ashkenazi, 2015). The low efficacy of conventional anti-DR5 antibodies has been attributed to lack of proper Fc γ R-mediated crosslinking, for example due to competition with endogenous serum IgG and/or absence of Fc γ R-expressing cells in the tumor microenvironment (Gieffers et al., 2013).

Of note, TAS266 is a particular multivalent anti-DR5 antibody fragment-based compound that was tested in humans. TAS266 is a tetravalent Nanobody[®], consisting of four humanized llamaderived VHH antibody fragments linked through 35-aa linkers (Huet et al., 2014). The TAS266 study was terminated after three out of four patients showed reversible liver toxicity at starting dose, which correlated with the presence of pre-existing anti-drug antibodies (ADA), suggesting that TAS266 toxicity was caused by an atypical antigenicity of the tetravalent Nanobody (Papadopoulos et al., 2015).

The unique concept and mechanism of action of GEN1029 supports the notion that GEN1029 is a promising therapeutic agent with potential anti-tumor effect in many different cancer types.

2.1.3 Summary of Nonclinical Studies

A comprehensive nonclinical data package is available supporting the mechanism of action (MoA) of GEN1029 to induce cell killing of DR5-positive cancer cells by DR5 hyperclustering and downstream caspase activation.

The individual antibody components of GEN1029, drug substances 1029-01 and 1029-05, bind different epitopes on DR5 but have comparable apparent binding affinities with EC50 values in the high picomolar/low nanomolar range. It was shown both *in vitro* and *in vivo* that GEN1029 induced more potent cytotoxicity compared to the single HexaBody molecules and to the mixture of wild type (WT) antibodies without the E430G mutation. These data demonstrated that both the mixture of the two different HexaBody molecules and the HexaBody format were required for the efficacy of GEN1029. Furthermore, it was demonstrated both *in vitro* and *in vivo* that the efficacy

of GEN1029 was independent of secondary Fc γ R-mediated crosslinking, which was in contrast to the conventional DR5-targeting antibody conatumumab. GEN1029 induced cytotoxicity *in vitro* in a range of cell lines derived from different solid cancers, with loss of cell viability starting at a median concentration (IC20) of 0.083 µg/mL (0.554 nM). *In vivo*, GEN1029 showed potent antitumor activity in a broad range of human cancer cell line-derived xenograft (CDX) models and consistently outperformed conatumumab in all responsive models. Maximal anti-tumor activity was observed at doses of 2 mg/kg or higher, and 0.5 mg/kg was the lowest dose at which antitumor activity in patient-derived xenograft (PDX) models, which are thought to represent the genetic and histological heterogeneity observed in human tumors.

The cytotoxic activity of GEN1029 was shown to be caspase-mediated. GEN1029 induced rapid and potent caspase-3/7 activation in DR5-positive cancer cells.

In vitro studies indicated that GEN1029 did not induce antibody-dependent cellular cytotoxicity (ADCC) or complement-dependent cytotoxicity (CDC) on tumor cell lines, and did not induce fluid-phase complement activation *in vitro*.

For more comprehensive information regarding nonclinical studies for GEN1029, please refer to the current version of Investigator's Brochure.

2.1.4 Summary of Clinical Trials

This will be the first administration of GEN1029 in humans; therefore, no clinical experience is available.

2.2 Rationale

Death Receptor 5 (DR5) is a receptor for Tumor Necrosis Factor Related Apoptosis-Inducing Ligand (TRAIL), which upon binding to the ligand, initiates an 'outside-in' signaling pathway leading to apoptotic cell death of TRAIL-sensitive cancer cells. While previously tested human DR5 monoclonal antibodies (mAbs) showed compelling pre-clinical anti-tumor activity, human DR5 mAbs did not perform well in clinical trials.

Receptor clustering and activation of apoptosis by human DR5 mAbs appeared not to be potent enough in patients, possibly due to insufficient crosslinking of DR5 via Fc γ R expressing immune cells in the tumor micro-environment. Fc γ R-mediated crosslinking is considered to be a key factor for the anti-tumor activity of human DR5 mAbs. Therefore, GEN1029 targeting of two distinct epitopes on DR5 with a mixture of two DR5-specific HexaBody molecules that organize into hexameric antibody structures upon surface target binding to increase Fc γ R-independent clustering is a rational novel approach to overcome this issue for the therapy of cancer patients.

Based on promising pre-clinical results this trial is planned to explore the safety, PK and biomarker profile as well as the anti-tumor activity of GEN1029 in patients with advanced and/or metastatic CRC, NSCLC, TNBC, RCC, gastric, pancreas or urothelial cancer who have failed available standard therapy or who are not candidates for standard therapy, and for whom, in the opinion of the investigator, experimental therapy with GEN1029 may be beneficial.

2.3 Benefit-Risk Assessment

Several human DR5 mAbs have been clinically tested but their anti-tumor effect has been rather limited presumably as a consequence of insufficient $Fc\gamma R$ -immune cell-mediated crosslinking of DR5 and a less potent apoptosis triggering signal (Micheau et al., 2013; Forero et al., 2017; Gieffers et al., 2013). GEN1029 targets two distinct epitopes on DR5 and enhances hexamer formation/receptor clustering in an $Fc\gamma R$ -independent manner and is therefore a rational novel approach to overcome this issue.

Previous clinically tested human DR5 mAbs have as described above generally been well tolerated and most adverse events (AEs) have been mild to moderate (CTCAE grade 1-2). The most frequently reported AEs across human DR5 mAb mono-therapy trials (Herbst et al., 2010; Doi et al., 2011; Camidge et al., 2010; Forero-Torres et al., 2010; Plummer et al., 2007; Wakelee et al., 2010; Forero et al., 2017) conducted in adult patients with advanced cancer disease are listed below (order reflecting reported frequency (x out of 7 trials)), independent of CTCAE grading:

Genmab

- Fatigue (among the most frequent reported AEs in 7/7 clinical trials)
- Nausea (6/7)
- Vomiting (6/7)
- Pyrexia (5/7)
- Anorexia (4/7)
- Anemia (3/7)
- Chills (3/7)
- Constipation (3/7)
- Cough (3/7)
- Diarrhea (3/7)
- Dyspnea (3/7)
- Headache (3/7)

The most frequent reported clinical significant and possibly drug related adverse event \geq grade 3 has been elevation of amino transferase liver enzymes (Camidge et al., 2010; Plummer et al., 2007). A mitigation plan for handling AEs of elevated liver parameters has been prepared for this trial in order to closely monitor, dose-delay, dose-reduce or withdraw patients with liver enzyme elevations (please see Section 7.2.2.1).

There are so far no specific experimental observations or knowledge about the reproductive or fetal developmental toxicity of GEN1029. However, DR5 mRNA has been described to be expressed in the reproductive system and reproductive effects of GEN1029 in humans can therefore not be ruled out. More detailed information about DR5 receptor expression, nonclinical and clinical results as well as potential safety aspects of GEN1029 therapy can be found in the Investigator's Brochure.

Based on nonclinical and clinical data available to date, and published data from other human DR5 mAbs, the conduct of the trial GCT1029-01 is regarded as justifiable. Furthermore, the patient population eligible for the current trial is patients with selected advanced and/or metastatic cancer, who have failed available standard therapy or who are not candidates for standard therapy, and for whom in the opinion of the investigator, experimental therapy with GEN1029 may be beneficial. All patients enrolled in this trial will be controlled frequently by qualified health care professional(s) who will provide care and closely monitor and evaluate the patient's response to the trial drug, in terms of its safety and efficacy.

As of the 20-Aug-2019, 27 patients have been exposed to GEN1029 at dose levels ranging from 0.3 to 3 mg/kg: 24 patients on the Biweekly Regimen (Q2W) and 3 patients on the Intensified Regimen ($8 \times Q1W/Q2W$). Based on this experience, two AEs have been identified as risks and AEs of special interest (AESIs). These are elevated transaminase levels and diarrhea (Section 10.3). As a result, a mitigation plan for handling AEs of diarrhea has been prepared for this trial to guide diagnostic steps and treatment.

Of note, all 3 patients exposed in the Intensified Regimen experienced DLTs due to transaminase elevations,

Consequently, the Intensified

Regimen is permanently discontinued.

More detailed information about the known and expected benefits and risks including reasonably expected AEs of GEN1029 can be found in the Investigator's Brochure.

3 OBJECTIVES AND ENDPOINTS

Objectives and related endpoints are described in Table 3-1.

Table 3-1 Objectives and Endpoints

Dose Escalation Part

Objectives			Endpoints		
Pri	mary				
•	Determine the MTD and/or the recommended Phase 2 dose (RP2D) Establish the safety profile of GEN1029	•	Dose limiting Toxicities (DLTs) Adverse events (AEs) and safety laboratory parameters (hematology and biochemistry)		
Sec	condary				
•	Establish the PK profile and evaluate immunogenicity of GEN1029 after single and multiple infusions	•	PK parameters (clearance, volume of distribution and area-under-the-concentration-time curve $[AUC_{0-Clast}$ and $AUC_{0-\infty}]$, $AUC0_14d$, CL. maximum concentration $[C_{max}]$, time of C_{max} $[T_{max}]$, pre-dose values, and half-life of GEN1029		
		•	Immunogenicity of GEN1029		
•	Evaluate the anti-tumor activity of GEN1029	•	Anti-tumor activity measured by tumor shrinkage (based on computerized tomography [CT]-scan evaluations)		
		•	Objective Response, Progression-Free Survival (PFS), Overall Survival (OS), Duration of Response (DoR), and Time to Response (TTR)		
Ex	ploratory				
•	To assess biomarkers predictive of response or resistance to GEN1029	•	DR5 expression (protein,) in tumor biopsies		
•	To assess potential pharmacodynamic biomarkers of	•	Circulating protein profiles		
	GEN1029	•	Immune cells levels		
		•	Biomarker profile		
•	To assess the metabolic response in the tumors	•	Standardized uptake volume corrected for body lean mass (SUL)		
•		•			

Expansion Part

	Objectives	Endpoints			
Pri	mary				
•	To evaluate the Objective Response Rate (ORR) by indication	• ORR			
Sec	condary				
	Evaluate the anti-tumor activity of GEN1029	• Anti-tumor activity measured by tumor shrinka (based on computerized tomography [CT]-so evaluations)	age can		
		• Objective Response, Progression-Free Survival (PF Overall Survival (OS), Duration of Response (Do and Time to Response (TTR)	'S), R),		
•	To further describe the safety profile of GEN1029	• Adverse events (AEs) and safety laboratory paramet (hematology and biochemistry)	ters		
	Evaluate the pharmacelyinetic (D K) profile as feasible	DV noremeters			
•	Evaluate immunogenicity of GEN1029 after single	• FK parameters			
and multiple infusions		Immunogenicity of GEN1029			
Ex	ploratory				
•	To assess biomarkers predictive of response or resistance to GEN1029	• DR5 expression (protein, DR5) in tun biopsies	nor		
•	To assess potential pharmacodynamic biomarkers of	Circulating protein profiles			
	GEN1029	Immune cells levels			
		Biomarker profile			
•	To assess the metabolic response in the tumors	• Standardized uptake volume corrected for body le mass (SUL)	ean		
•		•			

4 TRIAL DESIGN

4.1 Description of Trial Design

This is an open-label, multi-center phase I/IIa safety trial of GEN1029 in a mixed population of patients with solid tumor types. The trial consists of two parts; a dose escalation part (phase I, FIH) and an expansion part (phase IIa) as depicted in Figure 4-1.

Figure 4-1

In the dose escalation part, up to 2 dose regimens may be evaluated; these are described in Section 4.2. Those dose regimens, that are considered to be safe by the Data Monitoring Committee (DMC) and the sponsor safety committee, and for which a recommended phase 2 dose (RP2D) is established, may be further explored in the expansion part. Each expansion cohort will only include patients with one selected indication who are to be treated with one selected dose regimen. More than one dose regimen may be evaluated per indication, but in different cohorts.

Patients in both parts of the trial will receive treatment until disease progression. Thus, the treatment period will last until unacceptable toxicity or disease progression is observed. Efficacy will be assessed every six weeks primarily based on CT-scans. The RECIST 1.1 criteria will be used for response evaluation (Eisenhauer et al., 2009).

4.2 Dose regimens

This trial will evaluate a Biweekly Regimen (Q2W) and a Priming Regimen (Priming/Q2W), as described in Table 4-1. For both regimens, one cycle is 14 days.

Biweekly Regimen	Priming Regimen	
(Q2W)	(Priming/Q2W)	
Cycle 1–End of treatment Q2W	Cycle 1 – Priming dose on Day 1	
	Cycle 2– End of treatment	
	Q2W	

Table 4-1: Dosing Frequencies in the Two Dose Regimens

4.2.1 Biweekly Regimen (Q2W)

The trial is initiated with the Biweekly Regimen. In this dose regimen, patients are treated on day 1 of each cycle. The escalation of this regimen is started at 0.3 mg/kg and may thereafter evaluate GEN1029 at the following dose levels:

• 0.3, 1.0, 2.0, 3.0,

mg/kg

Dose escalations (and de-escalations) in the escalation part will follow the modified Bayesian Optimal Interval (mBOIN) design; see Section 4.3.

4.2.2 Priming Dose Regimen

Dose escalation based on a priming dose may be considered, applying dose levels that have been declared safe by the DMC and endorsed by the sponsor safety committee. The priming dose will be administered on Day 1 of the first cycle, and thereafter dosed with the maximum starting dose once every 14 days.

Scenarios for different priming and starting dose levels are covered in Table 4-2. The priming dose and the starting dose in Cycle 2 will be determined based on the totality of the available data and selected as recommended by the DMC and confirmed by the sponsor safety committee.

Dose escalation based on priming doses may potentially evaluate GEN1029 at the following dose levels in the second cycle (dependent on data collected during the trial):

• 0.3, , 1.0, 2.0, 3.0, mg/kg

Dose escalation (and de-escalations) in the escalation part will follow the mBOIN design; see Section 4.3.

4.3 Dose Escalation Part

In the dose-escalation part, there will be a minimum of 2 nights between the first and second patient in each dose cohort to account for any safety signals at each new dose level. This might be modified according to recommendations from the DMC and as endorsed by the sponsor safety committee. In addition, the first cohort of the Biweekly Regimen will be a single patient cohort. Furthermore, no other patients within a dose cohort will receive their first treatment simultaneously, i.e. on the same day, during the dose escalation part of the trial, unless apparently efficacious dose levels which are declared safe by the DMC are further investigated. During treatment, safety assessments will initially be performed on a weekly basis. For the assessments of each cohort, the DLTs will be collected for the first two cycles i.e. DLT period of 28 days. For the priming regimen, the DLT period must contain 14 days evaluation of one full dose administered after the priming dose have been administered. A patient is defined as "evaluable" if a DLT is observed prior to completing the DLT period, or if the DLT period is completed without any DLTs.

The dose escalation part will be performed as a mBOIN design (Yuan et al., 2016). This is in many ways similar to a traditional 3+3 design (even more similar to its 3+3+3 variant) except that the mBOIN design may allow re-escalation to an already investigated dose level. Re-escalation is allowed when the previous dose level is considered safe (based on data from additional patients). Re-escalation is not allowed to dose levels that have been terminated.

Specifically for this trial a target toxicity level of 30% has been chosen leading to escalation and de-escalation borders of lambda1=0.24 and lambda2=0.36.

According to the mBOIN design each time a cohort of patients has been completed, it is evaluated whether the next cohort should stay on the same dose, escalate to the dose level above or deescalate to the dose level below. This evaluation is based on the frequency of DLTs on the current dose level in the following way:

•	DLT frequency at current dose level ≤ 0.24 :	Escalate
•	DI frequency at current dose level >0.24 and <0.36 :	Stay at same dose level

De-escalate

• DLT frequency at current dose level >= 0.36:

After completion of the DLT period for each cohort, based on the safety data and the recommendation from the mBOIN design algorithm (Table 4-4), the DMC will recommend the dose-level for the next cohort of patients, see Table 4-3. As a precaution, the DMC can also recommend lower dose levels than the mBOIN design algorithm recommends and even below 0.3 mg/kg; i.e. 0.1 mg/kg.

Table 4-3 Number of DLTs Leading to Dose Escalation, De-escalation or Remaining at the Same Dose Level

Number of patients in a cohort	3	4	5	6	7	8	9
Escalate	0	0	<=1	<=1	<=1	<=1	<=2
Stay at same level	1	1	-	2	2	2	3
De-escalate	2	2	2	3	3	3	4
Terminate a dose level	3	>=3	>=3	>=4	>=4	>=4	>=5

First-in-Human Cohort:

In order to limit patients being treated at a dose of possibly limited efficacy (i.e. **Example**), the Biweekly Regimen (the initial regimen to be explored) will begin by evaluating GEN1029 with the initial cohort consisting of one evaluable patient (i.e. at 0.3 mg/kg). If this patient has experienced a DLT or \geq grade 3 toxicity (at least possibly drug-related), the cohort size will be increased to at least 3 evaluable patients.

Dose Level Termination:

A potential drawback of the basic BOIN design is that, theoretically, a very toxic dose level could be investigated in multiple cohorts, if the dose level just below it is not toxic. To avoid this problem, a dose level termination criterion is implemented (see Table 4-4).

Other mBOIN specific parameters are detailed in Table 4-4.

	Biweekly Regimen (Q2W)	Priming Regimen (Priming/Q2W)		
Target toxicity rate	30%			
[lambda1; lambda2]	[0.24; 0.36]			
DLT period	Day 1-28			
Stopping criteria	If the BOIN algorithm recommends that the next cohort should be run on a dose level that has already investigated 9 patients (to ensure that the trial will not keep enrolling patients on a dose level already adequately investigated)			
Dose level termination due to toxicity	A certain dose level can no longer be investigated if an additional DLT-free cohort would lead to de-escalation			
Default cohort size	3 pat	tients		
Initial cohort size	1 patient	3 patients		
Possibly modified cohort size	In case a cohort had less than 3 patients evaluable the next cohort on the same dose level may be enlarged to bring the number of patients on the dose level up to a multiple of 3			
Algorithm may be used if	There are at least 3 evaluable patients on a dose level (except the initial dose level)	There are at least 3 evaluable patients on a dose level		
Replacement of in- evaluable patients	If needed (to bring number of patients on the dose level up to 3) in-evaluable patients will be replaced.			
Over-recruitment on safe doses	Apparently efficacious dose levels which are declared safe by the DMC may be further investigated, augmenting the mBOIN design, by adding up to a total of max. 9 patients to such dose levels			
Maximum number of patients to add on safe doses	18			
DLT consideration in over- recruited patients	Do not contribute to mBOIN algorithm, but will be reported to DMC. (If the mBOIN algorithm later stipulates de-escalation to an over-recruited dose level, all patients on that dose will be counted as part of the mBOIN algorithm.)			

Table 4-4: Design Parameters of the mBOIN Design for the Two Dose Regimens

Determination of MTD and RP2D:

After the mBOIN algorithm has completed (for a given regimen), the DMC and the sponsor safety committee will determine the MTD and the RP2D which may be the same as the algorithm recommends for the next cohort or it may be a lower dose. In any case the RP2D will be a dose with a lower observed DLT rate than the target toxicity level of 30%.

If there is evidence that a dose level lower than the MTD (which might not have been reached at this stage) has adequate efficacy (whether determined by CT scan data or by pharmacodynamic endpoints or predicted efficacious dose) the DMC and sponsor safety committee may decide that the RP2D has been determined and may decide to stop the dose escalation.

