1 VISIT SCHEDULE

1.1 Dose Escalation Part

In the dose escalation part, up to 2 dose regimens may be evaluated:

- The Biweekly Regimen: patients are dosed once every 14 days (Q2W).
- The Priming Regimen: in the first cycle, patients receive a priming dose. After 14 days and thereafter, they are dosed with the maximum starting dose once every 14 days (Priming/Q2W).

An overview of the dosing frequency as well as treatment cycle duration and dose limiting toxicity (DLT) period duration, and scanning frequency is shown in Figure 1-1. A cycle is always 14 days and the DLT period is always 28 days, irrespective of which dose regimen the patients are following.

Further details on when the 2 dose regimens will be available and open for enrollment are described in Section 4.2.

Table 1-1 lists all of the assessments in the dose escalation part and indicates with an "X" the visits at which they are performed. All data obtained from these assessments must be supported in the patient's source documentation.

Table 1-2 shows the timing of the ECG assessments, Table 1-3 shows the timing of the PK sampling, Table 1-4 shows the timing of cytokine and complement sampling, and Table 1-5 shows the timing for measurement of vital signs in relation to infusions.

*: Mandatory PET-CT scans must be taken at screening and, if avid at screening, also at Cycle 2 Day 2, and week 12 (±7 days). If PET-CT at screening showed no avidity, a CT scan has to be done instead of a PET-CT in week 12 (±7 days).

: A CT scan must be performed at Cycle 3, Day 8-14 after first dose. From week 18 (\pm 7 days) until week 50 after first dosing, CT scans must be performed every 6 weeks (\pm 7 days), and every 12 weeks (\pm 7 days) thereafter. Imaging assessments should follow calendar days and should not be adjusted for delays in cycle starts. *: Only if a patient, who has been exposed to GEN1029, did not have any PET-CT scans while on treatment and displayed avidity at screening.

Figure 1-1 Overview of Dosing and Scanning Frequency, DLT and Cycle Duration – Dose Escalation Part

Treatment Cycle	Screening	Cycle 1-3 ¹			Cycle 4-PD ¹ End of treatment ²		Safety Follow-up ²¹		Patient follow-up	End of trial	Unscheduled		
Day	≤21 days prior to Visit C1-D1	1d	2d	3d ^{24,28}	8d	1d	8d ²²	-	30 days after last dosing	70 days after last dosing	13W, 26W, 39W + 52W after last dosing	-	-
Visit window ³		±1d	-	-	±1d	±3d	±1d	-	±7d	±7d	±14d	-	-
Informed Consent ⁴	Х												
Eligibility Criteria	Х												

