Demographics, disease status	Х												
Prior cancer therapy/surgery	Х												
Medical History	Х												
Height	Х												
Body Weight ⁶	Х	Х				Х		Х					
Physical Examination ²⁵	Х	Х				Х		Х					
Vital Signs ⁷	Х	Х	Х		Х	Х	Х	Х					X ¹⁴
Liver ultrasound	Х												
ECG						Plea	ise see Tal	ble 1-2 for detail	s of ECG asse	ssments			
PET-CT scan ²⁹	X ²⁹			X^8			X ⁸					X ³⁰	
Efficacy assessment (CT-Scan)				X ⁹			X ⁹	X ²³					X ¹⁴
ECOG status	Х	Х				Х		Х					X^{14}
Adverse Events ⁵	Х	Х	Х	Х	Х	Х	Х	Х	Х	Х	X ¹⁸		X^{14}
Concomitant Medication	Х	Х	Х	Х	Х	Х	Х	Х	X ¹⁹	X ¹⁹	X ¹⁹		X ¹⁴
Pre-medication ³³		Х	Х										
IMP administration		Х				Х							
End of trial												X ²⁰	
Laboratory assessments ¹⁰													I.
Hematology	Х	Х	Х		Х	Х	Х	Х	Х	Х			X ¹⁴
Biochemistry ²⁶	Х	Х	Х	X ²⁷	Х	Х	Х	Х	Х	Х			X^{14}
Urinalysis	Х	Х				Х		Х	Х	Х			X^{14}
							1		1	1			
Pregnancy Test ¹¹	X	X				X		X					X ¹⁴
ADA (Immunogenicity)	X	Х				X		X	X	X			X ¹⁴
Hepatitis B, C, CMV ¹²	Х			I		L			1 CDV	1.			X ¹⁴
PK Sampling	v 13	1	 	1	1	P.	lease see	1 able 1-3 for deta	alls of PK sam	ipiing	1		V 14
Tumor blopsy	Λ	V 15	+		V 15		V 17	A ^{···}					X ¹⁴
Immunophenotyping		Χ	1		D1		X''	Λ		lamont cor1			Λ
Cytokine and circulating factors		_			riea	se see 1	iule 1-4 IC	or details of cytol	cine and comp	iement sampli	ing		

Table 1-1 Visit evaluation schedule Dose Escalation Part – Biweekly Regimen (Q2W) and Priming Regimen (Priming/Q2W)

Footnotes to Trial Flowchart: Dose Escalation Part - Biweekly Regimen (Q2W) and Priming Regimen (Priming/Q2W)
¹ The duration of one cycle is 14 days. Treatment can continue until PD.
² If the patient shows PD, starts a new anti-cancer treatment or withdraws from treatment due to another reason, the end of treatment visit should be performed as soon as possible after decision of
discontinuation.
³ The specified visit windows are in accordance with the previous visit. However, within 28 days from treatment start (corresponding to the DLT period), max. 2 doses of GEN1029 in the O2W regimen and
in the priming regimen can be administered. At Cycles 2 and 3, Day 1 of the next cycle should be performed 7 days ± 1 day after Day 8 of the previous cycle and from Cycle 4 and onwards, Day 1 of the
next cycle should be performed 7 days ± 3 days after Day 8 of the previous cycle.
⁴ Informed consent must be obtained before or at Screening prior to making any screening assessments.
⁵ Adverse Events should be reported from the time the informed consent is signed.

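### Priming Regimen: the fixed Day 1-28 DLT period does not guarantee the 14 days of full-dose evaluation that Section 4.3 requires, and no available text says which rule prevails

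*Protocol*

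**What the plan says.** Section 4.3 first sets a common rule for each cohort: "the DLTs will be collected for the first two cycles i.e. DLT period of 28 days". It then adds a regimen-specific condition: "For the priming regimen, the DLT period must contain 14 days evaluation of one full dose administered after the priming dose have been administered". Its evaluability sentence follows. A patient is evaluable once a DLT has been seen, or "if the DLT period is completed without any DLTs".

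Elsewhere the period is a fixed calendar interval. Section 1.1 says "A cycle is always 14 days and the DLT period is always 28 days, irrespective of which dose regimen the patients are following". Table 4-4 gives Day 1-28 for both regimens, and Sections 7.1 and 11.4.1.1 also use 28 days. Table 1-1 footnote 3 fixes the starting point and limits dosing inside the interval: "within 28 days from treatment start (corresponding to the DLT period), max. 2 doses of GEN1029". In this regimen, treatment starts with the priming dose.

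SAP 4.3.3 places a subject in the Dose-Determining Set, and so counts the subject as evaluable for the MTD, if 80-125% of the planned dose was received and Day 1-28 was completed. It makes no exception for priming.

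On timing, footnote 3 measures windows from the preceding visit and says "Day 1 of the next cycle should be performed 7 days ± 1 day after Day 8 of the previous cycle". Table 1-1 gives the Day 8 visit its own ±1 day.

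**The concern.** The two rules agree only if the full dose is given by Day 15. After that, the 28 days end before 14 days of full-dose evaluation have accrued, and a patient can satisfy one rule while failing the other.

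The DLT count is the primary endpoint and the input to the mBOIN rule. Under the fixed-day rule, a DLT-type event inside the required 14 days but after Day 28 is not counted, which favours escalation. The boundary also governs care. Inside the DLT period, Section 7.1 requires the patient to stop drug. After it, Section 7.2.1.1 allows delay and possible re-treatment for a first grade 3 event, with separate rules for liver parameters.

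**Working it through.** **Inputs.** Full dose at Cycle 2 Day 1, nominally Day 15 (Sections 1.1 and 4.2.2). Period Day 1-28 from the priming dose (Table 4-4; Table 1-1 footnote 3). Cycle 1 Day 8 ±1 day, then 7 ±1 days to Cycle 2 Day 1 (Table 1-1). Target DLT rate 30% (Section 4.3). Table 4-3 for three patients: 0 DLTs, escalate; 1 DLT, stay.

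**1. On schedule.** Days observed = 28 − 15 + 1 = 14, dosing day included. This reproduces the 14 days in Section 4.3, with no slack.

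**2. Within the visit windows.** Full-dose day = (8 + a) + (7 + b), with a and b each −1, 0 or +1; days observed = 28 − full-dose day + 1.

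| Full-dose day | Combinations | Days observed |
|---|---|---|
| 13 | 1 | 16 |
| 14 | 2 | 15 |
| 15 | 3 | 14 |
| 16 | 2 | 13 |
| 17 | 1 | 12 |

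Three of nine fall below 14. Including the dosing day is the count more favourable to the protocol: without it, the on-schedule figure is 13 and six of nine fall short.

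**3. After a hold.** Table 7-3 requires drug to be held for grade 2 diarrhea, which by itself is not a DLT under Section 7.1. An assumed 7-day hold moves the full dose to Day 22 and leaves 28 − 22 + 1 = 7 days. The documents give neither the length nor the frequency of such holds; Section 7.3 stops treatment only when a toxicity delay exceeds 14 days.

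**4. What the choice of rule changes.** Take three patients, two of them DLT-free. The third has the full dose on Day 17 and a DLT-type event on Day 29, which is day 29 − 17 + 1 = 13 after the full dose.
- Fixed Day 1-28: 0/3, escalate.
- Two full cycles, with Cycle 2 running to Day 30: 1/3, stay.
- Fixed end at Day 28, but the 14-day condition needed for completion: two evaluable patients. Table 4-4 lets the algorithm run only if "There are at least 3 evaluable patients on a dose level", so a replacement is needed first.

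**5. Size.** Let s be the share of DLT risk that follows the full dose and m the part of that share falling after Day 28. For one short patient of three, P(0/3) = 0.70² × [1 − 0.30 × (1 − s × m)]. With full observation it is 0.70³ = 34.3%. The onset patterns are assumptions: even over 14 days, or early (80% in days 1-7, 20% spread over days 8-14).

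| Full dose | Onset | m | s = 1 | s = 0.5 |
|---|---|---|---|---|
| Day 17 | even | 2/14 = 0.143 | 36.4% (+2.1) | 35.4% (+1.1) |
| Day 17 | early | 0.2 × 2/7 = 0.057 | 35.1% (+0.8) | 34.7% (+0.4) |
| Day 22 | even | 7/14 = 0.5 | 41.7% (+7.4) | 38.0% (+3.7) |
| Day 22 | early | 0.2 | 37.2% (+2.9) | 35.8% (+1.5) |

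Shifts are in percentage points. For example, Day 17 with even onset and s = 1 gives 0.49 × (1 − 0.30 × 0.857) = 0.49 × 0.743 = 0.364.

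**The case against.** The strongest reply is that the specific sentence governs the general one. Twenty-eight days is then the nominal length, a priming period without 14 days of full-dose evaluation has not been completed, and a DLT-free patient in that position is inevaluable and can be replaced under Table 4-4. This is a natural reading and amounts to half of the proposed fix. But Section 1.1 says the period does not vary by regimen, and SAP 4.3.3 applies Day 1-28 without exception. Following that text leads to the opposite classification.

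A reader might infer from the conflict that the documents leave such a patient unclassified. They do not: read literally, Section 4.3 with the fixed period, together with the SAP rule, makes the patient evaluable. The defect is that this result does not enforce the 14-day requirement.

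A reader might also take three in nine as a rate of short patients. It only counts calendar combinations. The windows are symmetric, with three combinations above 14 days, three at 14 and three below, averaging 14. One or two days is ordinary visit tolerance.

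The safeguards are real. SAEs and non-serious events of grade 3 or higher reach the sponsor within 24 hours (Section 10.4.1), the DMC reviews cumulative safety data (Section 7.1), "the DMC can also recommend lower dose levels than the mBOIN design algorithm recommends", and the sponsor safety committee makes the dosing decision (Section 10.8). A Day 29 event reported before the cohort meeting could be seen. Section 6.4.1 also describes transaminase elevations as mainly a first-dose effect, which argues against placing all the risk after the full dose. These points limit the size of the problem but do not reconcile the two rules.

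**Conclusion.** The inconsistency stands and should be corrected, but its effect is small. At a 30% DLT rate with one short patient of three, the chance of 0/3 rises by 0.4 to 2.1 points at the latest permitted full-dose day. The figure of about 7 points requires an assumed 7-day hold, even onset and all risk after the full dose, so it is an upper scenario and not an expected bias.

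It would be tempting to conclude that the reported MTD is in doubt. The SAP does not support that: one subject is analysed under the Priming Regimen (SAP 3.3), that regimen appears in listings only (SAP 4.5), and nothing shows that this subject had a short window.

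The finding that no text settles precedence is limited to what could be read. The separate analysis-populations plan named in SAP 4.3.3 was not available, nor were the contents of Figure 1-1 and Table 4-2; any of them might resolve it.

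**What to change.** For the Priming Regimen, define the DLT period in Sections 1.1, 7.1 and 11.4.1.1, Table 4-4 and SAP 4.3.3 as ending at the later of Day 28 and completion of 14 days of evaluation after the first full dose. State that a DLT-free patient who does not reach that point is inevaluable and may be replaced under Table 4-4.

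Besides the wording changes, the cost is some waiting time. With the dosing day counted, the period ends at the later of Day 28 and full-dose day + 13: Day 28 in six of the nine window combinations, Day 29 in two and Day 30 in one. A full dose on Day 22 moves the end to Day 35, 7 days later. A hold at the 14-day limit (full dose on Day 29) moves it to Day 42, 14 days later, and replacing the patient may then be preferable. A cohort decision may wait that long, and an occasional patient will need replacing.
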